9.4. Selection and Timing of Doses

A cycle is defined as an interval of 21 days (up to 3 days delay of a cycle will be permitted due to holidays, weekends, bad weather, or other unforeseen circumstances and will not count as a protocol deviation).

Refer to Section 5.3.1 for the olaratumab dose rationale in this study.

The dose of olaratumab/placebo administered will be determined by measuring the patient's weight in kilograms on Days 1 and 8 of each cycle. The dose of doxorubicin administered will be determined by calculating the patient's body surface area (BSA) at the beginning of each cycle. If the patient's weight does not fluctuate by $\geq 10\%$ (increase or decrease) from the weight used to calculate the prior dose, the olaratumab/placebo dose will not need to be recalculated. A $\pm 5\%$ variance in the calculated total dose will be allowed for ease of dose administration.

Patients will receive combination treatment with olaratumab/placebo + doxorubicin for 8 cycles, followed by olaratumab/placebo as monotherapy until evidence of progressive disease (PD), unacceptable toxicity, death, or other withdrawal criteria are met.

9.4.1. Special Treatment Considerations

9.4.1.1. Dose Delays, Modifications, and Discontinuations

After treatment has been initiated, in order to **start** the **next** cycle the following criteria must be fulfilled:

- ANC $\geq 1.0 \times 10^3/\mu\text{L}$ (1000/ μL ; $\geq 1.0 \times 10^9/\text{L}$)

Note that in order to administer single-agent olaratumab/placebo on Day 8, ANC must be $\geq 750/\mu\text{L}$; $\geq 0.75 \times 10^9/\text{L}$. If the ANC is $< 750/\mu\text{L}$, the Day 8 administration of olaratumab/placebo may be delayed for a maximum of 7 days. If the ANC level has not increased to $\geq 750/\mu\text{L}$ within 7 days, then the Day 8 olaratumab/placebo dose in that cycle should be skipped and dosing resumed on Day 1 of the following cycle if criteria for dosing are met. If all dosing criteria are met, a delay or omission of the Day 8 olaratumab/placebo dose should not result in a delay of the Day 1 olaratumab/placebo dose of the following cycle.

- Platelets $\geq 100 \times 10^3/\mu\text{L}$ (100,000/ μL ; $\geq 100 \times 10^9/\text{L}$)
- Hemoglobin ≥ 8 g/dL
- Creatinine clearance ≥ 45 mL/min (refer to [Attachment 5](#) for the Cockcroft-Gault formula)
- Total bilirubin below ULN. In patients with Gilbert's syndrome, total bilirubin should be < 3 mg/dL.
- AST and ALT $\leq 3.0 \times \text{ULN}$, or $\leq 5 \times \text{ULN}$ if the transaminase elevation is due to liver metastases
- Nonhematologic toxicity must be less than Grade 2, except for those not deemed clinically significant by the investigator, or electrolyte abnormalities (for example, potassium, magnesium, phosphate).

Delays:

In general, dose delays of 1 study drug (olaratumab/placebo or doxorubicin) due to toxicity guidances outlined in Sections 9.4.1.1.1 and 9.4.1.1.2 will not necessitate delays of the other study drug.

To maintain a concomitant administration schedule of olaratumab/placebo and doxorubicin on Day 1 of the first 8 cycles, a delay in olaratumab/placebo administration will be allowed to match the corresponding delay in doxorubicin due to toxicity. For the same reason, a delay in doxorubicin administration will be allowed to match the corresponding delay in olaratumab/placebo due to toxicity. Treatment may be delayed for up to 21 days (1 equivalent cycle) to allow a patient sufficient time for recovery from study drug-related toxicity. If a patient does not recover from the toxicity within 42 days (2 equivalent cycles) from last dose, then the patient must be discontinued from study therapy.

Dose Modifications:

Any patient who requires a dose reduction will continue to receive the reduced dose for the remainder of the study. Any patient who has had 2 dose reductions and who experiences a toxicity that would cause a third dose reduction must be discontinued from study treatment.

Since all investigators are blinded to treatment arms, they will treat all patients as if the patient received study drug versus placebo and will adjust doses accordingly.

In the event of an alteration in olaratumab/placebo dose due to an olaratumab/placebo-related toxicity, doxorubicin need not be altered, and the planned doxorubicin schedule should be maintained.

Similarly, olaratumab/placebo therapy need not be altered or discontinued for doxorubicin-related toxicity. An alteration in doxorubicin dose will always necessitate a corresponding change in dexrazoxane dose, if administered, in order to maintain a dosage ratio of 10:1 (dexrazoxane:doxorubicin).

Discontinuations:

In general, discontinuation of 1 study drug (olaratumab/placebo or doxorubicin) will not necessitate discontinuation of the other study drug. Any changes in treatments being added to or removed from patient care will be recorded on the eCRF.

In the event of discontinuation of olaratumab/placebo therapy due to an olaratumab/placebo-related toxicity, doxorubicin need not be altered, and the planned doxorubicin schedule should be maintained. In the event that olaratumab/placebo treatment is discontinued for reason of toxicity, the patient may continue treatment with doxorubicin through Cycle 8 at the discretion of the investigator.

Similarly, olaratumab/placebo therapy should not be discontinued for doxorubicin-related toxicity. In the event that doxorubicin is discontinued for reason of toxicity, the patient may continue treatment with olaratumab/placebo until one or more discontinuation criteria are met, at the discretion of the investigator.

The following information (in this section and the following subsections) pertains to dose modifications and delays for and management of AEs of concern, which may or may not be associated with olaratumab/placebo therapy, including the following:

- IRR (see Section 9.4.1.1.1.1)
- Hematologic toxicity (see Section 9.4.1.1.1.2)
- Nonhematologic toxicity (see Section 9.4.1.1.1.3)

The following information (in this section and the following subsections) pertains to dose modifications and delays for and management of AEs of concern, which may or may not be associated with doxorubicin therapy, including the following:

- Hematologic toxicity (see Section 9.4.1.1.2.1)
- Cardiovascular toxicity (see Section 9.4.1.1.2.2)
- Hepatic impairment (see Section 9.4.1.1.2.3)
- Nonhematologic toxicity (see Section 9.4.1.1.2.4)

9.4.1.1.1. Olaratumab/Placebo

9.4.1.1.1.1. Infusion-Related Reactions

As with other monoclonal antibodies, hypersensitivity reactions may occur during or following olaratumab administration.

Patients treated with olaratumab/placebo should be closely monitored for signs and symptoms indicative of an infusion reaction by the medical staff from the start of the infusion until at least 1 hour after the end of the infusion in an area where emergency medical resuscitation equipment and other agents (epinephrine, prednisolone equivalents, etc.) are available.

Olaratumab/placebo infusion reactions will be defined according to the NCI-CTCAE version 4.0 definition of IRRs.

Symptoms occurring during or following infusion of investigational therapy may also be defined according to AE categories such as allergic reaction, anaphylaxis, or cytokine release syndrome (NCI-CTCAE version 4.0 section “Immune system disorders”). In the setting of symptoms or signs occurring during or following infusion of investigational therapy, investigators are encouraged to use the AE terms that best describe the event, and mark “yes” or “no” for hypersensitivity/IRR event flag.

For patients who experience a Grade 1 or 2 IRR, the infusion should be stopped and the patient treated with the following (or equivalent) medications: a histamine H1 antagonist (eg, diphenhydramine) and glucocorticoid (eg, dexamethasone) intravenously, acetaminophen, and oxygen (as indicated), according to standard medical practices. After recovery, the infusion rate should be decreased 50% for the duration of the infusion. After a Grade 1 or 2 IRR, patients should be premedicated with the following (or equivalent) medications: a histamine H1 antagonist (eg, diphenhydramine) and glucocorticoid (eg, dexamethasone) intravenously, and acetaminophen, as appropriate, approximately 30-60 minutes prior to all subsequent olaratumab/placebo infusions.

A Grade 3 or 4 IRR will require immediate treatment, including the use of epinephrine, bronchodilators, and/or glucocorticoids for symptomatic bronchospasm, IV fluids and/or

pressors for hypotension, and immediate and permanent discontinuation of olaratumab/placebo with appropriate supportive care.

If a patient experiences an IRR to olaratumab/placebo, all attempts should be made to obtain an anti-olaratumab/placebo antibody blood sample as close to the onset of the event as possible, at the resolution of the event, and 30 days (± 3 days) following the event. In addition, these same samples may be assessed for levels of olaratumab and for pharmacodynamic markers to provide information on the nature of the IRR. The procedure for sample collection and handling is described in a separate procedural manual.

9.4.1.1.1.2. Hematologic Toxicity

Table JGDJ.2 summarizes the olaratumab dose modifications required in case of hematological toxicities.

Table JGDJ.2. General Guidelines for Olaratumab/Placebo Dose Modification Due to Hematologic Toxicity Deemed Related to Olaratumab/Placebo

Toxicity	Required Dose Modification
Neutropenia	
ANC Grade 1-3	No dose modification required
ANC <500 cells/ μ L (Grade 4)	No treatment administered; treatment cycle delayed
At retreatment:	
If \geq Grade 3 neutropenic fever/infection has occurred	Withhold dose until ANC is 1000 cells/uL or higher; reduce dose to 12 mg/kg (15 mg/kg if toxicity occurs during Cycle 1).
If Grade 4 neutropenia lasting longer than 1 week has occurred	Withhold dose until ANC is 1000 cells/uL or higher; reduce dose to 12mg/kg (15 mg/kg if toxicity occurs during Cycle 1).
Grade 4 ANC without fever/infection	Retreatment with olaratumab/placebo at full dose at investigator's discretion with recommended use of prophylactic G-CSFs
Second incidence of either: 1) \geq Grade 3 neutropenic fever/infection 2) Grade 4 neutropenia lasting longer than 1 week	Second dose reduction to 10 mg/kg
Thrombocytopenia	
Platelets <100,000 cells/ μ L	No treatment administered; treatment delayed until resolved to \geq 100,000 cells/ μ L
Anemia	
Hemoglobin <8 gm/dL	No treatment administered; treatment delayed until resolved to \geq 8 gm/dL

Abbreviations: ANC = absolute neutrophil count; G-CSFs = granulocyte colony-stimulating factors.

9.4.1.1.1.3. Nonhematologic Toxicity

Specific guidelines for dose adjustments in patients who experience olaratumab/placebo IRRs may be found in Section 9.4.1.1.1.1.

General guidelines for dose modification for other nonhematologic toxicities related to olaratumab/placebo are shown in [Table JGDJ.3](#). If more than 2 toxicity-related olaratumab/placebo dose reductions are required, treatment with this agent will be permanently discontinued.

Table JGDJ.3. General Guidelines for Dose Modification Due to Nonhematologic Toxicities Related to Olaratumab/Placebo

Reaction Grade	Required Dose Modification
Grade 1	No dose modification is required.
Grade 2	At the investigator's discretion, the patient may continue to receive olaratumab/placebo per protocol, provided that the event does not pose a serious health risk or is easily treated.
Grade 3	For a Grade 3 toxicity not adequately controlled with appropriate supportive care, the dose must be withheld until toxicity is \leq Grade 1 or has returned to pretreatment baseline; then treatment may resume at a reduced dose of 12 mg/kg (15 mg/kg if the toxicity occurs during Cycle 1). If toxicity recurs after therapy resumes, a second dose reduction (to 10 mg/kg) is permitted.
Grade 4	The dose must be withheld until dose toxicity is \leq Grade 1 or has returned to baseline. Permanent discontinuation should be considered for any patient experiencing Grade 4 nonhematological toxicity assessed as related to olaratumab/placebo. However, if resumption of dosing is deemed appropriate by the investigator, treatment may resume only after consultation with the Lilly study physician, with the dose reduced to 10 mg/kg (15 mg/kg if the toxicity occurs during Cycle 1). If Grade 4 toxicity recurs after therapy resumes, olaratumab/placebo treatment will be discontinued.

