9.4.1.1.2. Doxorubicin

9.4.1.1.2.1. Hematologic Toxicity

Doxorubicin will not be administered after the initial dose if the patient's ANC is <1000 cells/ μL or if the platelet count is $<100,000$ cells/ μL . When necessary, the next treatment cycle should be delayed until the ANC is ≥ 1000 cells/ μL and the platelet count is $\geq 100,000$ cells/ μL and nonhematologic toxicities have resolved. For patients who experience \geq Grade 3 neutropenic fever or infection or Grade 4 neutropenia without fever lasting more than 1 week, doxorubicin should be reduced to 75% of the starting dose (that is, to approximately 60 mg/m²). If a patient experiences a second incidence of neutropenic fever/infection or has another episode of Grade 4 neutropenia lasting >1 week, then a second dose reduction to 45 mg/m² will be necessary. Therapeutic and prophylactic use of Neulasta[®] (pegfilgrastim) or other G-CSFs will be allowed per current American Society of Clinical Oncology (ASCO; Smith et al. 2006) and National Comprehensive Cancer Network (NCCN) guidelines (NCCN 2014). For patients with Grade 4 ANC without fever/infection lasting less than 1 week, retreatment will be allowed at the investigator's discretion with the full dose of doxorubicin (75 mg/m²) with recommended use of G-CSFs per current ASCO guidelines (Smith et al. 2006). See [Table JGDJ.4](#) for doxorubicin dose modification for neutropenia.

Table JGDJ.4. General Guidelines for Doxorubicin Dose Modification Due to Neutropenia

Toxicity	Required Dose Modification
ANC <1000 cells/ μ L	No doxorubicin administered; treatment cycle delayed.
At retreatment:	
If \geq Grade 3 neutropenic fever/infection has occurred	Approximately 60 mg/m ² doxorubicin.
If Grade 4 neutropenia lasting longer than 1 week has occurred	Approximately 60 mg/m ² doxorubicin.
Grade 4 absolute neutrophil count (ANC) without fever/infection	Retreatment with doxorubicin at full dose at investigator's discretion with recommended use of prophylactic G-CSFs.
Second incidence of either:	Second dose reduction to 45 mg/m ² .
1) \geq Grade 3 neutropenic fever/infection	
2) Grade 4 neutropenia lasting longer than 1 week	

9.4.1.1.2.2. Cardiovascular Toxicity

Cardiotoxicity is a recognized risk of doxorubicin that increases with higher cumulative drug exposure. Cardiac monitoring is conducted by a combination of monitoring of clinical parameters, ECG, and echocardiogram (ECHO) / multigated acquisition (MUGA) scan.

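### Table JGDJ.2 gives two conflicting olaratumab/placebo instructions for afebrile Grade 4 neutropenia lasting more than 1 week

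*Protocol*

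**What the plan says.** Section 9.4.1.1.1.2 of the Protocol consists of one introductory sentence, "Table JGDJ.2 summarizes the olaratumab dose modifications required in case of hematological toxicities", and the table. The table is confined to toxicity judged related to olaratumab/placebo. Three of its neutropenia rows matter here:

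- "If Grade 4 neutropenia lasting longer than 1 week has occurred": withhold until the neutrophil count is at least 1000/µL, then reduce to 12 mg/kg (15 mg/kg for a Cycle 1 event).
- Grade 4 count with neither fever nor infection: "Retreatment with olaratumab/placebo at full dose", at the investigator's discretion, with prophylactic G-CSF recommended.
- Second incidence of febrile or infected neutropenia of Grade 3 or higher, or of Grade 4 neutropenia of more than 1 week: "Second dose reduction to 10 mg/kg".

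Section 9.4.1.1 makes reductions permanent: "Any patient who requires a dose reduction will continue to receive the reduced dose for the remainder of the study". It also requires discontinuation when a toxicity would call for a third reduction.

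For doxorubicin, Section 9.4.1.1.2.1 deals with duration in its text. In "Grade 4 neutropenia without fever lasting more than 1 week, doxorubicin should be reduced to 75% of the starting dose" it sends long afebrile episodes to reduction. It then limits full dose: "For patients with Grade 4 ANC without fever/infection lasting less than 1 week, retreatment will be allowed". The matching row of Table JGDJ.4, "Retreatment with doxorubicin at full dose", omits that limit.

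**The concern.** The reduction row depends on duration and is silent on fever. The full-dose row depends on absence of fever and infection and is silent on duration. An afebrile Grade 4 episode of more than 1 week satisfies both. One site can reduce and another can retreat at full dose after the same event, each pointing to a row of the same table.

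The event is foreseeable. Sections 5.3 and 5.3.1 report more neutropenia with olaratumab plus doxorubicin in the Phase 2 study, and list neutropenia among the Grade 3 or higher events seen in at least 10% of the olaratumab arm. Investigators are blinded and must manage every patient as if on active drug, so the ambiguity operates in both arms. What is at stake is a safety instruction after prolonged severe neutropenia, the patient's running count of reductions, and the consistency of the planned summaries of reductions and dose intensity (Protocol 12.2.5; SAP 5.2.1.2).

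**Working it through.** The plan has no statistical figure to reproduce here. The check compares the rows and then works out the dose consequence.

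**Step 1. Sort first Grade 4 episodes by fever/infection and duration.**

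| Episode | Reduction row (more than 1 week) | Full-dose row (no fever/infection) |
|---|---|---|
| Afebrile, 1 week or less | not met | met |
| Afebrile, more than 1 week | **met** | **met** |
| Febrile or infected, more than 1 week | met | not met |

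Neither row is the more specific one: each adds a condition on which the other is silent.

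**Step 2. Look for a rule of precedence.** Section 9.4.1.1.1.2 has no text beyond the introductory sentence and the table. The general rules in 9.4.1.1 give count thresholds, delay limits and the cap on reductions, but do not separate the two rows. Attachment 9 reprints the table with the same wording in these rows, so the overlap is not a text-extraction fault. The SAP does not address it.

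**Step 3. Compare doxorubicin.** The text of 9.4.1.1.2.1 resolves the same overlap: reduce to about 60 mg/m² beyond 1 week, full dose below 1 week. It names doxorubicin only, and 9.4.1.1 treats dose changes for the two drugs separately. Followed as written, the doxorubicin text leaves no dose difference. Two loose ends remain. Table JGDJ.4 does not repeat the limit. And an episode of exactly 1 week falls in neither limb of the text; only the table's full-dose row covers it.

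**Step 4. Dose consequence** (doses from Table JGDJ.2 and the 15 mg/kg planned from Cycle 2).

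- First episode after Cycle 1: 12/15 = 0.80, so 20% lower under the reduction row.
- Second episode of more than 1 week, full dose kept the first time: 10/15 = 0.667, a 33% drop in one step, under a row that calls it a second reduction although there was no first.
- Second episode, dose reduced the first time (after Cycle 1): 10/12 = 0.833, a 17% drop.
- Cycle 1 episode retreated at Cycle 2: 15 versus 15 mg/kg, no dose difference. Whether a reduction is counted can still differ.
- Cycle 1 episode affecting a delayed Day 8 dose, if one is given: 15/20 = 0.75, so 25% lower under the reduction row.

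In each first-episode case the patient's count of permanent reductions can differ by one, and so can the distance from mandatory discontinuation.

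**The case against.** The strongest reply is that the table has only one sensible reading. The retreatment rows can be read as a cascade: fever or infection first, then long Grade 4 episodes, then whatever Grade 4 remains. If the full-dose row also took long afebrile episodes, the long-episode row would be left almost entirely with febrile or infected patients, who already get the same action from the row above. The second-incidence row assumes that the first long episode was reduced, and the doxorubicin text spells out the same rule for the same patient. Moreover, the reduction row is an instruction under a column of required modifications, while the full-dose row is only a permission.

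This is good evidence of intent, and I accept that reduction is the likely intent. It is not a stated rule. The table does not say that its rows are to be applied in order, and a site that uses the full-dose row is still following a row whose conditions are met.

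Three further points stand as limits on size. The case is narrow: Grade 4, afebrile, more than 1 week, attributed to olaratumab/placebo and, for the 20% difference, after Cycle 1. Attribution is itself a judgement that can already make dosing differ between similar episodes. And a step from 15 to 10 mg/kg is not unique to this conflict, because a Cycle 1 event reduced to 15 mg/kg leads to the same step at a second incidence.

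**Conclusion.** The concern holds. For afebrile Grade 4 neutropenia of more than 1 week related to olaratumab/placebo, the protocol states two incompatible actions and no precedence. For first events after Cycle 1 the difference is 20% of the dose and one permanent reduction; at a second episode it is a 33% rather than a 17% step. These figures assume that the patient was on the planned 15 mg/kg and that the sites choose different rows. The documents give no basis for estimating how many patients this would affect.

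The consequences are bounded. A new cycle cannot start below 1000/µL under either row, the primary survival analysis and the statistical design are untouched, and doxorubicin dosing is settled by its own text. This is a correction that should be made because it concerns a safety dosing rule; it does not threaten the trial's conclusions.

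**What to change.** In Table JGDJ.2, add *lasting 1 week or less* to the label of the full-dose row, so that longer episodes fall only under the reduction row. Make the same addition in Table JGDJ.4. In the text of 9.4.1.1.2.1, change the limit for full-dose doxorubicin from under 1 week to *1 week or less*, so that an episode of exactly 7 days is assigned.

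The cost is a few words in two table rows and one sentence. No procedure, visit or analysis changes, and apart from assigning the exact 7-day case the rule is the one the sponsor already wrote for doxorubicin.

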9.4.1.1.2. Doxorubicin

9.4.1.1.2.1. Hematologic Toxicity

Doxorubicin will not be administered after the initial dose if the patient's ANC is <1000 cells/ μL or if the platelet count is $<100,000$ cells/ μL . When necessary, the next treatment cycle should be delayed until the ANC is ≥ 1000 cells/ μL and the platelet count is $\geq 100,000$ cells/ μL and nonhematologic toxicities have resolved. For patients who experience \geq Grade 3 neutropenic fever or infection or Grade 4 neutropenia without fever lasting more than 1 week, doxorubicin should be reduced to 75% of the starting dose (that is, to approximately 60 mg/m²). If a patient experiences a second incidence of neutropenic fever/infection or has another episode of Grade 4 neutropenia lasting >1 week, then a second dose reduction to 45 mg/m² will be necessary. Therapeutic and prophylactic use of Neulasta[®] (pegfilgrastim) or other G-CSFs will be allowed per current American Society of Clinical Oncology (ASCO; Smith et al. 2006) and National Comprehensive Cancer Network (NCCN) guidelines (NCCN 2014). For patients with Grade 4 ANC without fever/infection lasting less than 1 week, retreatment will be allowed at the investigator's discretion with the full dose of doxorubicin (75 mg/m²) with recommended use of G-CSFs per current ASCO guidelines (Smith et al. 2006). See [Table JGDJ.4](#) for doxorubicin dose modification for neutropenia.

Table JGDJ.4. General Guidelines for Doxorubicin Dose Modification Due to Neutropenia

Toxicity	Required Dose Modification
ANC <1000 cells/ μ L	No doxorubicin administered; treatment cycle delayed.
At retreatment:	
If \geq Grade 3 neutropenic fever/infection has occurred	Approximately 60 mg/m ² doxorubicin.
If Grade 4 neutropenia lasting longer than 1 week has occurred	Approximately 60 mg/m ² doxorubicin.
Grade 4 absolute neutrophil count (ANC) without fever/infection	Retreatment with doxorubicin at full dose at investigator's discretion with recommended use of prophylactic G-CSFs.
Second incidence of either:	Second dose reduction to 45 mg/m ² .
1) \geq Grade 3 neutropenic fever/infection	
2) Grade 4 neutropenia lasting longer than 1 week	

9.4.1.1.2.2. Cardiovascular Toxicity

Cardiotoxicity is a recognized risk of doxorubicin that increases with higher cumulative drug exposure. Cardiac monitoring is conducted by a combination of monitoring of clinical parameters, ECG, and echocardiogram (ECHO) / multigated acquisition (MUGA) scan.

ECG changes, arrhythmias, tachycardia, and/or chest pain should be managed according to clinical practice based on the specific findings.

Patients will undergo baseline LVEF determination by ECHO or MUGA scan. This evaluation may be repeated at any time during the study if clinically indicated. A decrease in LVEF of $\geq 10\%$ and below the lower limit of normal, or an absolute decrease of 20%, or if the absolute LVEF decreases to or below 40%, then doxorubicin will be discontinued. Doxorubicin should also be discontinued if the patient develops Grade 3 or 4 left ventricular systolic dysfunction (symptomatic congestive heart failure). If doxorubicin is discontinued for the above changes in LVEF, the patient may continue on study with olaratumab/placebo, provided that the patient meets all other entry criteria (see Section 9.4.1.1).

The diagnostic method used at baseline for cardiovascular assessments (for example ECHO or MUGA scans) should be the same method used throughout the study, unless there is clinical or instrumental evidence that further investigations are needed.

9.4.1.1.2.3. Hepatic Impairment

Doxorubicin is contraindicated in patients with severe hepatic impairment (Child-Pugh Class C or total serum bilirubin >5.0 mg/dL). Refer to Section 9.4.1.1 for additional information.

9.4.1.1.2.4. Nonhematologic Toxicity

Permanent discontinuation of doxorubicin should be considered for any patient experiencing Grade 4 nonhematologic toxicity assessed as related to doxorubicin. If the investigator feels re-dosing of doxorubicin is appropriate (except for Grade 4 cardiotoxicities and Grade 4 bilirubin increase which require mandatory discontinuation [see Section 9.4.1.1.2.2 and Section 9.4.1.1.2.3]), treatment may only resume after consultation with the Lilly study physician, with

the dose reduced to 60 mg/m² (or less if agreed by the investigator and Lilly physician). If Grade 4 toxicity recurs after therapy resumes, doxorubicin treatment will be permanently discontinued.

For appropriate management of cardiac toxicities and hepatic impairment, refer to Section 9.4.1.1.2.2 and Section 9.4.1.1.2.3.

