9.6.1.1. Dexrazoxane

Starting with Cycle 1, dexrazoxane may be administered IV at the investigator's discretion according to instructions provided in the Pharmacy Manual for this study, beginning within 30 minutes prior to each doxorubicin infusion for the prevention of cardiotoxicity. It is recommended that all patients receiving 5 or more cycles of doxorubicin receive dexrazoxane. Investigators should consult the dexrazoxane information provided in the Pharmacy Manual for

this study for administration information (including warnings, precautions, contraindications, adverse reactions, and dose modifications).

Note that as the dose of dexrazoxane administered is dependent on the dose of doxorubicin administered, any dose modifications to doxorubicin will require a corresponding dose modification to dexrazoxane in order to maintain a dosage ratio of 10:1 (dexrazoxane:doxorubicin).

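### The first doxorubicin reduction for neutropenia is given as 75% of the starting dose and glossed as about 60 mg/m², which is 80%; the percentage is most likely the error

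*Protocol*

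**What the plan says.** Doxorubicin starts at 75 mg/m² on Day 1 of each 21-day cycle, for up to 8 cycles (Protocol Synopsis; Sections 8.1 and 9.1).

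Section 9.4.1.1.2.1 sets the reductions for neutropenia. After Grade 3 or worse neutropenic fever or infection, or Grade 4 neutropenia without fever lasting more than a week, "doxorubicin should be reduced to 75% of the starting dose (that is, to approximately 60 mg/m"². (The quotations from this part of the Protocol stop just before the superscript 2.) After a second such event, "then a second dose reduction to 45 mg/m"² is required. The paragraph ends by sending the reader to Table JGDJ.4 "for doxorubicin dose modification for neutropenia". In that table, the column headed Required Dose Modification gives about 60 mg/m² for each of the two first-event triggers and 45 mg/m² for the second event. It gives no percentage.

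Three other rules bear on the point:

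- **Carry-forward (Section 9.4.1.1):** "Any patient who requires a dose reduction will continue to receive the reduced dose for the remainder of the study".
- **Dexrazoxane (Sections 9.4.1.1 and 9.6.1.1):** "An alteration in doxorubicin dose will always necessitate a corresponding change in dexrazoxane dose", where it is given, to hold the 10:1 ratio.
- **Grade 4 nonhematologic toxicity (Section 9.4.1.1.2.4):** if re-dosing is agreed, it resumes with "the dose reduced to 60 mg/m"² or less. This is a separate rule.

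This is current text. The revised sections reproduced in Attachment 9 do not include Section 9.4.1.1.2.1.

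**The concern.** The sentence offers a percentage and a dose as equivalents, and they are not. It is an operative dosing instruction for a cytotoxic drug, used after an episode of serious or prolonged neutropenia. A pharmacist who multiplies the starting dose by 0.75 prepares a different dose from one who reads the mg/m² figure or the table. Because a reduced dose is kept for the rest of treatment, the difference would recur in each later cycle and pass to dexrazoxane where that is used.

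**Working it through.** **Inputs.** Starting dose 75 mg/m² (Synopsis, Section 9.1); stated fraction 75% and stated dose about 60 mg/m² (Section 9.4.1.1.2.1); second step 45 mg/m² (same section and Table JGDJ.4); dexrazoxane ratio 10:1 (Section 9.6.1.1); permitted variance of ±5% in the calculated total dose (Section 9.4).

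**1. Trying to reproduce the stated dose.** 0.75 × 75 = 56.25 mg/m², not 60. In the other direction, 60 / 75 = 0.80. A dose of 60 mg/m² would be 75% of 60 / 0.75 = 80 mg/m², which is not the starting dose here.

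**2. Size of the gap.** 60 − 56.25 = 3.75 mg/m². This is 3.75 / 60 = 6.25% of the higher figure and 3.75 / 56.25 = 6.67% of the lower. For an assumed body surface area of 1.6 to 2.0 m², it is 3.75 × 1.6 = 6.0 mg to 3.75 × 2.0 = 7.5 mg per dose.

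**3. Which figure fits the rest of the rule.**

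| First level | Step down from 75 | Step down to 45 |
|---|---|---|
| 60 mg/m² | 15 | 15 |
| 56.25 mg/m² | 18.75 | 11.25 |

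For this reduction, the 75% figure appears once. About 60 mg/m² appears three times: in the sentence and in two table rows.

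**4. Does rounding explain it?** 56.25 rounds to 56 at the nearest whole number and to 55 at the nearest 5. It reaches 60 only at the nearest 10, and the 45 mg/m² step does not follow that grid.

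**5. Does the ±5% variance cover it?** Around 56.25 the band is 53.4 to 59.1 mg/m²; around 60 it is 57 to 63 mg/m². The bands overlap from 57 to 59.1, but neither nominal dose lies inside the other's band. This assumes that the variance applies to doxorubicin. It is stated in a paragraph that covers both drugs, without saying which.

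**6. Carry-forward.** At 10:1, dexrazoxane would be 562.5 against 600 mg/m², a gap of 37.5 mg/m². The most that can accumulate for doxorubicin is with Cycles 2 to 8 all given at the first reduced level and no second reduction: 75 + 7 × 56.25 = 468.75 against 75 + 7 × 60 = 495 mg/m². That gap is 26.25 mg/m², or 26.25 / 495 = 5.3%.

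**7. Reach into the analysis.** SAP Section 5.2.1.2 fixes planned doxorubicin intensity at 25 mg/m² per week whatever the reduced level. A reduced cycle given on schedule would show a relative dose intensity of (56.25 / 3) / 25 = 75% or (60 / 3) / 25 = 80%. That is a descriptive summary of what was given. No test uses it.

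**The case against.** The strongest reply is that the dose is clear in practice. The sentence explains its own percentage as "approximately 60 mg/m"², and the table it cites gives only that dose under its required modification. 56.25 mg/m² is printed nowhere. A site would have to pass over both the parenthesis and the table to give it. Most of this stands. It is why the percentage, and not the dose, is taken as the likely error, and why the point is minor. It does not make the sentence correct.

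A reader might infer more: that the Protocol sets two competing dose levels with nothing to choose between them, so that sites would split. The documents do not support that. No clause states an order of precedence, and the title of Table JGDJ.4 calls its contents general guidelines. Even so, the gloss, the table and the equal steps all point the same way.

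A reader might also note that 60 is marked as approximate, while the 45 mg/m² step and the 60 mg/m² in Section 9.4.1.1.2.4 are not, and take that as a sign of a rounded 75%. The pattern is real, but the rounding needed is to the nearest 10, so this is weak evidence.

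Finally, Section 5.3.1 reports more neutropenia with olaratumab plus doxorubicin in the earlier Phase 2 study. A reader might infer that the slip could bias the comparison between arms. Nothing in the documents says how many patients would meet the trigger, or that any site would dose from the percentage. The rule and the gap per patient are the same in both arms.

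**Conclusion.** The sentence is wrong as written: 75% of 75 mg/m² is 56.25 mg/m², and 60 mg/m² is 80%. That part is plain arithmetic. That 60 mg/m² is the intended dose, and 75% a slip for 80%, is an inference. It is well supported, but the sponsor has to confirm it.

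The difference is 3.75 mg/m² per reduced cycle for a site that uses the percentage. It exceeds the ±5% variance if that variance covers doxorubicin. The cumulative difference of 26.25 mg/m² is a ceiling, not an expectation. The number of patients affected cannot be derived from the documents. The point is minor, and alpha, power and the overall survival analysis do not depend on it.

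**What to change.** Ask the sponsor to confirm that the first reduced level is 60 mg/m². Then, in the sentence in Section 9.4.1.1.2.1, change 75% to 80% or delete the percentage and leave the mg/m² figure. Table JGDJ.4, the 45 mg/m² second step and Section 9.4.1.1.2.4 need no change, and neither does the SAP.

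The cost is one number in one Protocol sentence. It affects neither sample size nor analysis.
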